Carvedilol as an adjunct to endoscopic cyanoacrylate injection for secondary prophylaxis of gastric variceal bleeding

Protocol ID: VGHKS11-CT10-11

ClinicalTrials.gov ID: NCT02504723

Principle investigator: [name]

Division of Gastroenterology and Hepatology, Department of Internal Medicine,

Kaohsiung Veterans General Hospital,

[name]

[contact] [name]; [contact]; Email: [contact]

Document date: Dec. 12, 2011

Materials and methods

Patients

Cirrhotic patients presenting with acute GVB were evaluated for eligibility.

The inclusion criteria were:

- (1) age of 20 to 80 years;
- (2) cirrhotic patients with acute GVB proven by endoscopy within 24 h of bleeding;
- (3) stable hemodynamic condition for at least 3 days after a cyanoacrylate injection.

The exclusion criteria were:

- (1) previous treatment for gastric varices (GV), including endoscopic therapy, transjugular intrahepatic porto-systemic shunt (TIPSS), or shunt surgery;
- (2) contraindications to NSBBs or cyanoacrylate injection;
- (3) serum total bilirubin > 10 mg/dL;
- (4) grade III/IV hepatic encephalopathy;
- (5) hepatorenal syndrome;
- (6) severe heart failure (NYHA Fc III/IV);
- (7) chronic kidney disease under renal replacement therapy;
- (8) refractory ascites;
- (9) malignancy other than hepatocellular carcinoma;
- (10) pregnancy;

(11) the use of a pacemaker;

(12) refusal to participate.

Randomization was performed when the hemodynamic conditions were stable, usually 3 to 5 days after initial GVO for acute bleeding. A computer-generated randomization sequence in a 1:1 ratio was used for randomization. The randomization sequences were concealed until after the patients had given consent to participate in the study and the interventions had been assigned.

The patients randomized to group A underwent repeated GVO until the varices were completely obturated. The patients randomized to group B received carvedilol in addition to repeated GVO.

General management

Patients were resuscitated with red cells and crystalloid solution. Terlipressin 1 g q6h for 3 days was immediately started on arrival at the emergency room. Prophylactic antibiotics were administered for 5 days and were adjusted according to sensitivity tests in the patients proven to have an infection. After GVO, esomeprazole 40 mg intravenous infusion twice daily was administrated for 2 days, and then shifted to oral esomeprazole 40 mg daily until the ulcers associated with GVO had completely healed.

Endoscopic therapy

The patients underwent emergency GVO whenever possible, usually 4 to 12 hours after presentation. GVO was performed using an XQ-260 or H-260 endoscope (Olympus Optical Co. Ltd., Tokyo, Japan) and a 22-gauge disposable injection needle (EIS 01943, Top Co., Tokyo, Japan) with a mixture of N-butyl-2-cyanoacrylate (Histoacryl blue, Braun, Melsungen, Germany) and lipiodol (Guerbet Laboratory, Aulnay-Sous-Bris, France) in a 1:1 ratio. The maximum amount of N-butyl-2-cyanoacrylate injected was usually 2 mL per session. GVO was performed at 3- to 4-week intervals during follow-up endoscopy, with the aim of eradicating the GV. GV was considered to be complete obturated when a firm consistency of the injected GV was noted in probing with the tip of the injection needle. The patients then underwent endoscopic ultrasonography to evaluate the status of obturation if scar tissue could not be differentiated from patent GV as previously described.¹ The total amount of N-butyl-2-cyanoacrylate and the number of treatment sessions required to obliterate the GV were recorded. The patients underwent follow-up endoscopy at 6-month intervals after obturation of GV. GVO was performed if recurrent GVB was encountered or GV recurred. Banding ligation was performed using Saeed[®] multi-band ligators (Cook Medical, Bloomington, IN) or Speedband Superview Super 7TM multiple band ligators (Boston Scientific, Marlborough, MA) for primary or secondary prophylaxis of EVB in patients with high-risk EV if they agreed.

Carvedilol administration

Carvedilol was started immediately after randomization in the patients assigned to group B at a dose of 6.25 mg daily. Patients underwent dose escalation every 3 days during the admission or every 7 days in the out-patient clinics until the maximum tolerated dose was achieved or up to 25 mg daily, with the goal of reducing the resting pulse rate by 25% but not less than 55 bpm while the systolic blood pressure was greater than 90 mm Hg. Adherence to the regimen was carefully assessed at each follow-up visit by questioning the patient and his or her relatives and counting the tablets where possible.

Management of rebleeding

The patients with recurrent GVB underwent emergency GVO. Emergency banding ligation was performed in the patients with EVB. The patients with uncontrolled variceal bleeding underwent TIPSS unless otherwise contraindicated.

Study end-points

The primary end-point of this trial was the occurrence of recurrent GVB. The secondary end-points were recurrent upper gastrointestinal bleeding, mortality or liver transplantation, and adverse events associated with both therapies.

Statistical analysis

The proposed sample size was 60 cases in each group.

Demographic data were compared between both groups. Categorical data were compared using the chi-square test or Fisher's exact test as appropriate. Continuous variables with normal distribution were compared using independent Student's t-tests, and continuous variables without normal distribution were compared using the Mann-Whitney U test. Kaplan-Meier analysis was conducted to examine the time from enrollment to the recurrence of GVB, UGIB, and mortality. A log-rank test was used to examine variations between groups. Univariate and multi-variate analyses using Cox's proportional hazards model were used to examine the risk factors associated with recurrent GVB, UGIB, and mortality. Significance was defined as $p < 0.05$ for all two-tailed tests.

References

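### Out-patient titration gives group B up to about 2 to 3 early contacts with no written counterpart in group A, so mild adverse events may be detected more often in group B

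*Combined protocol and SAP*

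**What the plan says.** The Patients section sets out the two regimens: "The patients randomized to group A underwent repeated GVO until the varices were completely obturated" and "The patients randomized to group B received carvedilol in addition to repeated GVO". No placebo or blinding is described.

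The contacts written for both arms are in the Endoscopic therapy section: "GVO was performed at 3- to 4-week intervals during follow-up endoscopy, with the aim of eradicating the GV". After obturation, endoscopy follows every 6 months.

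The Carvedilol administration section adds contacts for group B only. "Carvedilol was started immediately after randomization in the patients assigned to group B at a dose of 6.25 mg daily", and "Patients underwent dose escalation every 3 days during the admission or every 7 days in the out-patient clinics". Escalation stops at the highest dose the patient tolerates, with 25 mg a day as the ceiling. The target is a 25% fall in resting pulse, with a floor of 55 bpm and a systolic pressure above 90 mm Hg. The same section mentions follow-up visits, without a timetable, when it describes how adherence to the carvedilol regimen is checked.

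Under Study end-points, "The secondary end-points were recurrent upper gastrointestinal bleeding, mortality or liver transplantation, and adverse events associated with both therapies". The plan gives no schedule, checklist or assessor for adverse events in either arm. The Statistical analysis section names general tests for categorical and continuous data, and Kaplan-Meier and log-rank methods for time to bleeding and death.

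**The concern.** The titration rule cannot be applied without asking about tolerance and measuring pulse and systolic pressure. Group B therefore has low pulse, low pressure and intolerance looked for at each titration contact. Nothing written prompts the same enquiry in group A before its first repeat GVO. Neither patients nor staff are described as blinded, so the design has no other feature that evens out observation.

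At stake is the between-arm reading of adverse events. Part of any excess of mild events in the carvedilol arm could reflect more frequent contact, and the data as planned would not allow the two explanations to be separated. Counting every event regardless of cause would not help, because the difference arises before an event is recorded.

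**Working it through.** The plan's only design figure is 60 patients per group. It is given without event rates, power or follow-up length, so it cannot be reproduced, and this point does not rest on it.

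**Step 1. When the first shared visit falls.** Repeat GVO comes 3 to 4 weeks (21 to 28 days) after the initial GVO (Endoscopic therapy). Randomization is usually 3 to 5 days after the initial GVO (Patients). The first repeat GVO therefore falls between 21 − 5 = 16 and 28 − 3 = 25 days after randomization.

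**Step 2. Weekly contacts before that visit.** If titration is wholly out-patient, contacts fall on days 7 and 14, and on day 21 if GVO is late. That is 2 to 3 in group B and none written for group A.

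**Step 3. Whether titration lasts that long.** The step size from 6.25 to 25 mg is not stated. If each step doubled the dose there would be 2 steps (2 × 7 = 14 days out-patient). If each step added 6.25 mg there would be 3 (3 × 7 = 21 days). Both are assumptions for counting only, and both agree with 2 to 3 contacts. In-patient steps, or reaching the tolerated dose early, would reduce the number.

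**Step 4. Illustration of size.** Everything in this step is assumed: a true incidence of 25% in both arms, a chance p that any one visit records the event, and independent visits. The recorded rate after k visits is 25% × [1 − (1 − p)^k]. Group A has only the shared visits; group B has those plus 2 to 3. For p = 0.4 and one shared visit, group A records 25% × 0.40 = 10.0%. Group B records 25% × 0.784 = 19.6% (k = 3) to 25% × 0.870 = 21.8% (k = 4).

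| Shared visits counted | p | Group A | Group B | Excess (points) |
|---|---|---|---|---|
| 1 | 0.4 | 10.0% | 19.6 to 21.8% | 9.6 to 11.8 |
| 1 | 0.7 | 17.5% | 24.3 to 24.8% | 6.8 to 7.3 |
| 2 | 0.4 | 16.0% | 21.8 to 23.1% | 5.8 to 7.1 |
| 2 | 0.7 | 22.8% | 24.8 to 24.9% | 2.0 to 2.2 |
| 3 | 0.4 | 19.6% | 23.1 to 23.8% | 3.5 to 4.2 |
| 3 | 0.7 | 24.3% | 24.9 to 25.0% | 0.6 to 0.7 |

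**Step 5. What unequal detection does to a test.** Take 60 per arm, a two-sided 5% level, a pooled two-proportion test and equal true rates between 10% and 40%. Under the normal approximation, the chance of a false significant difference depends on the share of group B's detection that group A achieves:

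| Group A detects, relative to B | Chance of a false significant difference |
|---|---|
| 100% | 5% |
| 90% | 5 to 7% |
| 75% | 8 to 21% |
| 50% | 18 to 67% |

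The documents do not show which row applies.

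**The case against.** The strongest reply is that much of the imbalance is read from silence. The plan gives no clinic timetable for either arm beyond titration and endoscopy. A reader might infer that group A went unseen until its first repeat GVO, but the documents do not say so. What stands is narrower: contacts are written for one arm only, so equal observation is not secured.

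A reader might also count the 3-day escalation steps as extra contact. They take place during admission, when a group A patient still in hospital is under observation too. Only the weekly clinic contacts count. They are confined to the first weeks, after which the written endoscopy schedule is the same in both arms.

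It is tempting to put the spurious excess at 7 to 12 points. That range follows only if a single shared visit is counted. The model also treats an event as present and equally detectable at every visit, which fits transient events poorly.

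A further inference would be that the bleeding end-points are seriously biased. The documents do not support this. Under Management of rebleeding, recurrent variceal bleeding is treated as an emergency, so it would usually surface in either arm. Extra detection in group B would count against carvedilol and could not create a false benefit.

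Finally, the adverse-event end-point is limited to events associated with the therapies, and no specific between-arm test of it is named. A symptomless low pulse in a group A patient may fall outside it. This weakens the point but does not remove it: a comparison of symptoms such as dizziness would still rest on unequal enquiry.

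**Conclusion.** The concern holds for mild adverse events during out-patient titration. Followed as written, the plan gives group B up to about 2 to 3 early contacts at which tolerance, pulse and systolic pressure are assessed. It writes no equivalent contact or common enquiry for group A. The count assumes wholly out-patient titration and the usual timing of randomization.

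The direction is predictable: mild events may be detected more often in group B. The size is not. Under the assumed figures the excess runs from 0.6 to 11.8 points, depending mainly on detection per visit and on how many shared visits are counted. The effect on recurrent bleeding is likely small, and the documents give no ground for extending the point to a false benefit on the primary end-point. The point goes beyond a missing detail, because a cheap change at visits both arms already attend would reduce the bias.

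**What to change.** - At every shared visit (3- to 4-weekly GVO and 6-monthly endoscopy), complete the same checklist in both arms: symptoms, pulse, systolic pressure and interval bleeding history. Ask about symptoms since the last shared visit, so that the recall period is equal.
- Record emergency attendances and admissions in both arms.
- Keep all adverse events in the main safety report, including those found at titration visits, and flag the type of visit at which each was found.
- Add a supplementary between-arm comparison limited to events found at shared visits or through emergency attendance or admission.

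The restricted comparison should stay supplementary. If titration-visit events were dropped from the main comparison, genuine early reactions to carvedilol that resolve before the next GVO could be lost and harm understated.

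The cost is one protocol paragraph, a short form at existing visits and one extra analysis. No dose, clinical rule or number of visits changes.

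### Does leaving liver transplantation out of the Kaplan-Meier and Cox sentences require a change to the plan?

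*Combined protocol and SAP*

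**What the plan says.** Under Study end-points, recurrent gastric variceal bleeding (GVB) is primary. The next sentence reads: "The secondary end-points were recurrent upper gastrointestinal bleeding, mortality or liver transplantation, and adverse events associated with both therapies".

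Under Statistical analysis, the time-to-event method is given as: "Kaplan-Meier analysis was conducted to examine the time from enrollment to the recurrence of GVB, UGIB, and mortality". The next sentence adds: "A log-rank test was used to examine variations between groups". The Cox models "were used to examine the risk factors associated with recurrent GVB, UGIB, and mortality". A general sentence in the same section says: "Categorical data were compared using the chi-square test or Fisher's exact test as appropriate". Significance is set at p < 0.05 "for all two-tailed tests".

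Apart from titles in the reference list, the end-point sentence is the only mention of liver transplantation. The document gives no censoring rule of any kind.

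**The concern.** The end-point list pairs death with transplantation, and the analysis sentences keep only death. If the pair is one composite, its time-to-event analysis is not spelled out. If it is two outcomes, transplantation has no named time-to-event analysis, and the mortality curve has no rule for transplanted patients.

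Three rules are possible: censor at transplant (A), follow the patient through transplant and count later death (B), or count death or transplant, whichever comes first (C). They can give different event counts and p-values from the same 120 patients. A choice left until the data are seen could be made to suit the result. Censoring at transplant could also be informative if sicker patients are the ones transplanted.

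**Working it through.** **Plan figures.** No number in the plan depends on this point. The only design figure is "The proposed sample size was 60 cases in each group", or 2 × 60 = 120 patients. It comes without event rates, effect size, power or follow-up, so it cannot be reproduced. Assumed rates of 40% v 17% at 80% power and 40% v 14% at 90% power both give 60 per group.

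**Text side by side.**

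| Study end-points | Kaplan-Meier and Cox | Other cover |
|---|---|---|
| Recurrent GVB | named | – |
| Recurrent upper gastrointestinal bleeding (UGIB) | named | – |
| Death / transplantation | death named | categorical-data sentence can compare transplant proportions |
| Adverse events | not named | categorical-data sentence |

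The three time-to-event outcomes follow the order of the end-points. An analyst may therefore take the third as a short label for the paired end-point (rule C). Or the analyst may take it literally as death (rule A or B) and compare transplant counts separately. The categorical-data sentence directly follows one on demographic data and names no outcome. It is nevertheless the only test available for adverse events, so reading it as covering outcomes is reasonable.

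**Does the choice damage the comparison?** All inputs here are assumed: 1:1 allocation, 3-year follow-up, death hazard 0.15/yr, transplant hazard 0.01, 0.02 or 0.04/yr (about 3, 6 or 12 transplants in 120), log-normal frailty with SD 0.8 multiplying both hazards, and post-transplant death hazard 0.08/yr. Carvedilol does not affect transplantation unless stated. The test is a two-sided 0.05 log-rank. The frailty is not scaled to mean 1, so 0.15/yr is a median and the mean is 0.15 × exp(0.8²/2) ≈ 0.21/yr.

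| Quantity | ~3 | ~6 | ~12 transplants |
|---|---|---|---|
| No effect: p < 0.05, each rule alone | 4.9–5.2% | 4.9–5.2% | 4.9–5.2% |
| No effect: at least one of A, B, C | 6.5% | 7.2% | 8.0% |
| Conditional death HR 0.6: rules disagree | 9.6% | 13.4% | 18.1% |
| HR 0.6: power, rule A | 29.1% | 28.7% | 28.4% |
| HR 0.6: power, rule C | 26.7% | 24.4% | 21.2% |

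Large-sample results, transplant hazard 0.02 and 0.04/yr:

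- Arm HR under rule A is 0.632–0.635, against 0.637–0.638 with no transplants. The shift is at most 0.638 − 0.632 = 0.006.
- Under rule A, 3-year Kaplan-Meier mortality falls by 0.6 points with 5% transplanted and 1.1 points with 10%. The fall is 0 if transplantation is unrelated to risk and up to 2.2 points with strong selection.
- The rule C HR is 0.686 and 0.721, because it also counts an event that the drug is assumed not to affect.

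**How far the assumptions move this.** With about 0.3 or 1 transplant in 120, the at-least-one figure is 5.2% or 5.8% and disagreement is 2.2% or 4.8%. With death hazard 0.05/yr and transplant hazard 0.04/yr, the at-least-one figure is about 10%. With frailty scaled to mean 1, disagreement is 8.4%, 12.1% and 15.7%.

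**Would fixing on the composite gain anything?** Schoenfeld: power = Φ(½√d × |ln HR| − 1.96). For 30 events and HR 0.5: ½√30 × 0.693 − 1.96 = −0.06, giving 47.5%. Adding 12 transplants as events with the same HR: ½√42 × 0.693 − 1.96 = 0.29, giving 61.3%. If the drug does not affect transplantation, the table above shows power falling instead. The direction depends on something the documents do not settle.

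**The case for a change.** The strongest case for a change is that the mismatch is real, and that one sentence would close it at no cost in data. Calling the shorter wording shorthand is an inference. Under the assumed inputs, the verdict at 0.05 depends on the rule in roughly 10–18% of trials. The missing rule also reaches beyond this end-point: the recurrent GVB and UGIB curves are equally silent on follow-up after transplant, so the primary analysis is clear of the wording mismatch but not of the silence. If transplantation were twice as frequent in one arm (18% v 10%) with no effect on death, rule A would give HR 0.97 and rule C 1.17.

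The wording gap stands, and so does its reach to the GVB and UGIB curves. The rest is weaker. The 6.5–8.0% arises only if someone runs all three analyses and picks one; whichever rule is used alone, the error rate is about 5%. Disagreement at 0.05 is a poor yardstick when power is only 21–29%, and rule C differs from A and B because it asks another question. With unequal transplantation the death comparison stays close to 1, and the composite moves because it counts transplants, as it is meant to. Since transplantation is a listed end-point, a difference in counts by arm would be there to see. A competing-event analysis would be a reasonable extra, but with so small an expected shift it is a preference.

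**Conclusion.** The concern is accurate as a reading of the text and does not call for a change. Followed as written, the plan gives a sound comparison of deaths. Transplantation is recorded as an end-point and can be compared as a proportion, and each sensible rule gives a test of about the right size. Under the assumed inputs, the expected distortion of the arm hazard ratio from censoring at transplant is at most 0.006, and the mortality curve shifts by about 1 percentage point or less with up to 10% transplanted (2.2 points with strong selection).

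This rests on transplants being few or similar between arms and on the analyst using one rule rather than choosing among several. The documents give no death rate, transplant rate or follow-up length, so neither condition can be checked from them, and none of the simulated percentages estimates what this trial will show. What remains is a point of wording, with no demonstrated error in any result.

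### The only adverse-event end-point, read literally, counts just therapy-attributed events, so group A gives no background rate for carvedilol-type symptoms

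*Combined protocol and SAP*

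**What the plan says.** The Study end-points section lists three kinds of secondary end-point: recurrent upper gastrointestinal bleeding, mortality or liver transplantation, and "adverse events associated with both therapies". The last is the only adverse-event text in the end-points or the analysis. The document gives no adverse-event definition, causality rule, assessor or collection schedule.

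On treatment, the Patients section gives group A repeated cyanoacrylate obturation (GVO) and states: "The patients randomized to group B received carvedilol in addition to repeated GVO". Neither a placebo nor masking after assignment is described. The Carvedilol administration section adds a contact schedule for group B: "Patients underwent dose escalation every 3 days during the admission or every 7 days in the out-patient clinics".

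The visits described for both arms are in the Endoscopic therapy section: "GVO was performed at 3- to 4-week intervals during follow-up endoscopy", and later "The patients underwent follow-up endoscopy at 6-month intervals after obturation of GV".

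The Statistical analysis section says "The proposed sample size was 60 cases in each group" and "Kaplan-Meier analysis was conducted to examine the time from enrollment to the recurrence of GVB, UGIB, and mortality". The Cox models cover the same three outcomes. Adverse events could fall only under the general sentence on chi-square or Fisher tests for categorical data.

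**The concern.** The trial asks whether carvedilol is worth adding to GVO. Part of the answer is how much non-fatal harm it adds over GVO alone. Randomization makes that measurable: group A shows how often drug-type symptoms arise anyway in cirrhotic patients after a bleed, and the difference between arms is the excess.

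An end-point limited to attributed events discards that background rate. GVO-attributed events can occur in both arms, but carvedilol-attributed events can occur only in group B. The comparison then depends on someone who apparently knows the treatment deciding, without a stated rule, which symptoms the drug caused. Background symptoms may be credited to carvedilol, or real drug effects may be put down to cirrhosis and dropped.

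**Working it through.** **1. Which reading does the text support?** The General management section uses the same words causally, for acid suppression continued "until the ulcers associated with GVO had completely healed". That favours the literal reading of the end-point. Against it, the Statistical analysis section uses associated with in a purely statistical sense for risk factors, and the therapies in question could simply be the two regimens. The literal reading is supported but not proved. Steps 2 and 3 apply only on that reading.

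**2. Carvedilol-attributed events.** Only n = 60 per arm comes from the protocol. That figure has no stated basis to reproduce, and this point does not dispute it. All rates below are assumptions.

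Let p0 be the background risk of drug-type symptoms in both arms, d the extra risk caused by carvedilol (treated as additive), a the share of background events in group B attributed to carvedilol, and q the share of carvedilol-caused events so attributed. Group A scores zero.

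- Recorded difference = a × p0 + q × d. True difference = d.
- Error = a × p0 − (1 − q) × d.

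| Assumptions | Error at p0 = 10% / 20% / 30% (points) |
|---|---|
| d = 0, a = 0.5 | +5 / +10 / +15 |
| d = 10 points, a = 0, q = 0.5 | −5 / −5 / −5 |
| d = 10 points, a = 0.25, q = 0.5 | −2.5 / 0 / +2.5 |

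The error is zero when attribution is perfect (a = 0, q = 1), or by cancellation as in the last row at 20%. Attributed counts alone cannot show which case applies.

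**3. One pooled count of GVO- and carvedilol-attributed events.** Let g be the GVO-event risk in both arms, independent of symptoms, with d = 0, p0 = 20% and a = 0.5. Group B risk = 1 − (1 − g)(1 − 0.20 × 0.5).

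| g | A | B | Spurious excess | Fisher p < 0.05 (exact, 60 per arm) |
|---|---|---|---|---|
| 10% | 10% | 19% | 9 points | 20% of trials |
| 20% | 20% | 28% | 8 points | 12% |
| 30% | 30% | 37% | 7 points | 9% |

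The plan does not commit to this test. The last column only shows what applying it would do.

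**4. Precision when drug-type symptoms are counted in both arms.** Newcombe 95% intervals for a 10-point excess at 60 per arm:

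- 6/60 v 12/60: −3.0 to 22.9 points
- 12/60 v 18/60: −5.5 to 24.9
- 18/60 v 24/60: −6.9 to 26.2

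Sampling error is therefore as large as, or larger than, most of the errors in steps 2 and 3. A confidence interval displays sampling error but not attribution error.

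**5. Why a single any-event total is not the answer.** If other events occur independently in a share o of patients in both arms, an excess d in drug-type symptoms appears in the any-event proportion as (1 − o) × d. For d = 10 points and o = 50%, 60% or 70%, that is 5, 4 or 3 points.

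**6. Unequal contacts.** Out-patient escalation every 7 days falls between endoscopies 3 to 4 weeks apart: days 7 and 14 within 21 days (2 contacts), or days 7, 14 and 21 within 28 days (3 contacts). While titration lasts, group B may have up to 2 to 3 more occasions per interval to report a symptom. Group A's clinic schedule is not stated.

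**The case against.** The strongest objection is that the phrase is ambiguous and the bias exists on one reading only. That stands: what is certain is that the end-point is undefined, and the attribution problem is conditional. It does not remove the need for a change, because the two readings give different counts and the documents choose neither.

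Second, no adverse-event comparison is specifically planned, so attributed events might only be tabulated. This also stands. It rules out a reading that a reader might infer, that the plan tests carvedilol-attributed events in group B against a structural zero in group A. At 60 per arm such a test would be alarming: with a 20% risk in both arms and half of group B's events attributed, it is significant in 56% of trials. But the plan does not specify it.

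Third, a reader might infer a particular direction, such as carvedilol harm being exaggerated because treatment is known. The documents give no event rates, attribution shares or masking statement from which a direction could be derived. Larger negative errors can be produced by supposing that group A's drug-type symptoms are blamed on GVO more often than group B's, but nothing in the text supports that.

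Fourth, counting everything could swap one fault for another: other events dilute a drug effect, and extra titration contacts inflate group B's count. Both are right (steps 5 and 6) and they shape the remedy.

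**Conclusion.** The point holds in a limited form. On the literal reading, any between-arm comparison of non-fatal drug-type symptoms would depend on attribution that cannot be checked, and could be biased either way. The illustrations run from −5 to +15 points, but every rate in them is assumed; the documents give neither size nor direction. The point rests on the literal reading of the phrase and on inferring absence of masking from the lack of any placebo or blinding text; the protocol does not call itself open-label.

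It would go too far to conclude that the trial's safety assessment as a whole is invalid. Recurrent gastric variceal bleeding (the primary end-point), recurrent upper gastrointestinal bleeding, and mortality or transplantation carry no attribution condition and are untouched. This is a worthwhile correction to one secondary end-point.

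**What to change.** - Reword the end-point as all adverse events in both arms, regardless of attribution. This also settles the matter if the looser reading was intended.
- Ask the same questions in both arms at the follow-up endoscopies already scheduled, during obturation and afterwards.
- Compare arms by event type, with drug-type symptoms (for example dizziness, hypotension or bradycardia) separate from GVO-type events. Give each as a risk difference with a 95% confidence interval.
- Base that comparison on events elicited at the visits common to both arms. List events found only at group B titration contacts separately.
- Report therapy-attributed events descriptively. An any-event total may be shown, but not as the main comparison.

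If data collection is complete, apply this as far as the records of both arms allow and state the limit.

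The cost is wording, somewhat more recording in group A and a longer table; no visit is added. Some limits remain and should be stated. Self-report without masking can still differ by arm, mild events may be forgotten over 6-month intervals, and precision at 60 per arm is modest.

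### Kaplan-Meier is the only planned estimator of time to rebleeding and nothing is said about death or transplantation first, so the rebleeding probabilities would be overstated in each arm

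*Combined protocol and SAP*

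**What the plan says.** Under Study end-points, "The primary end-point of this trial was the occurrence of recurrent GVB". Death is not part of it. Death and transplantation appear only as a separate secondary end-point, "mortality or liver transplantation", listed after recurrent UGIB.

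Under Statistical analysis, "Kaplan-Meier analysis was conducted to examine the time from enrollment to the recurrence of GVB, UGIB, and mortality". For the comparison of arms, "A log-rank test was used to examine variations between groups". Cox models are planned for risk factors of the same three outcomes. Chi-square or Fisher's exact tests are planned for categorical data in general and are not assigned to the primary end-point.

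The document contains no censoring rule, no cumulative incidence function, no competing-risk model and no composite of rebleeding or death. Transplantation is in the secondary end-point but not in the Kaplan-Meier sentence, so its role in every time-to-event analysis is undefined. No follow-up length and no expected event rate are stated.

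**The concern.** A patient who has died cannot rebleed, and transplantation ends or fundamentally changes the risk under study. Kaplan-Meier assumes that a censored patient could still have the event later, at the same rate as those who remain under observation. If death and transplantation are treated as censoring, one minus Kaplan-Meier estimates a rebleeding risk in a hypothetical setting where nobody dies or is transplanted. That is higher than the proportion of patients who actually rebleed.

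Only death or transplantation before the first rebleed matters here; a death after rebleeding does not compete. Such events are plausible in this trial. The patients have cirrhosis with acute GVB, hepatocellular carcinoma is not an exclusion, and the plan itself expects enough deaths to analyse mortality by Kaplan-Meier and Cox.

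The Kaplan-Meier curve is the only planned time-based description of the primary end-point. Any rebleeding percentage, absolute difference or number needed to treat read from it would inherit the error.

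**Working it through.** **Inputs.** From the documents: the Kaplan-Meier plan, the separate end-points and 60 patients per arm. The documents give no event rates, so all hazards and time points below are assumptions. The plan states no rebleeding figure that could be reproduced.

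**Formulae.** Let *b* be a constant yearly hazard of GVB, *d* a constant yearly hazard of death or transplantation before rebleeding, and *t* the time in years.

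- With competing events censored: 1 − KM = 1 − exp(−*bt*)
- Actual probability of rebleeding: CIF = [*b*/(*b*+*d*)] × [1 − exp(−(*b*+*d*)*t*)]

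Worked example, *b* = 0.20, *d* = 0.05, *t* = 2: 1 − exp(−0.40) = 33.0%, against (0.20/0.25) × [1 − exp(−0.50)] = 31.5%.

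**Per-arm overstatement at 2 years**

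| *b* | *d* | 1 − KM | CIF | Excess (points) |
|---|---|---|---|---|
| 0.10 | 0.05 | 18.1% | 17.3% | 0.8 |
| 0.20 | 0.05 | 33.0% | 31.5% | 1.5 |
| 0.30 | 0.05 | 45.1% | 43.1% | 2.0 |
| 0.10 | 0.10 | 18.1% | 16.5% | 1.6 |
| 0.20 | 0.30 | 33.0% | 25.3% | 7.7 |
| 0.30 | 0.30 | 45.1% | 34.9% | 10.2 |

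At 1 year, over the same range of *b*, the excess is 0.2 to 0.6 points for *d* = 0.05 and 0.5 to 3.4 points for *d* = 0.10 to 0.30.

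**Arm difference at 2 years.** Take *b* = 0.20 in the control arm and 0.10 in the carvedilol arm. Kaplan-Meier gives 33.0 − 18.1 = 14.8 points (from unrounded values) whatever the death and transplantation rates are. The CIF difference depends on them:

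| *d*, control | *d*, carvedilol | CIF, control | CIF, carvedilol | Difference (points) |
|---|---|---|---|---|
| 0.05 | 0.05 | 31.5% | 17.3% | 14.2 |
| 0.20 | 0.20 | 27.5% | 15.0% | 12.5 |
| 0.30 | 0.20 | 25.3% | 15.0% | 10.2 |
| 0.10 | 0.20 | 30.1% | 15.0% | 15.0 |
| 0.10 | 0.30 | 30.1% | 13.8% | 16.3 |

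Differences are taken before rounding. The Kaplan-Meier difference can therefore be too large or too small.

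**Sampling error, for scale.** The 95% half-width of a 33.0% versus 18.1% difference with 60 per arm is 1.96 × √(0.330 × 0.670/60 + 0.181 × 0.819/60) = 15.4 points.

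**Checks by simulation.**

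- *Direction.* In 4,000 simulated arms of 60, with assumed net risks of 40% for rebleeding and 30% for death, one minus Kaplan-Meier was never below the Aalen-Johansen estimate. The mean excess was 5.9 points, against 5.8 by formula.
- *The test.* In 4,000 simulated trials of 60 per arm with an assumed uniform 1 to 4 years of follow-up, GVB hazard was 0.20 in both arms and death or transplantation 0.30 versus 0.15. The log-rank test rejected in 5.1%, so its type I error is sound. Mean 2-year one minus Kaplan-Meier was 33.0% and 32.9%; mean Aalen-Johansen was 25.3% and 28.7%.

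**The case against.** The strongest reply is that the problem is descriptive and conditional. The plan does not say that deaths are censored, and it does not commit to a fixed-time percentage, an absolute difference or a number needed to treat. The log-rank test and Cox model are untouched. Crude proportions compared by chi-square or Fisher's test may also be reported, and these carry no Kaplan-Meier inflation. The size rests wholly on assumed rates. Exclusions such as hepatorenal syndrome and "refractory ascites" remove some high-risk patients, and at a competing hazard of 0.05 the arm difference moves only from 14.8 to 14.2 points. Even the largest shift shown, 14.8 to 10.2, is well inside the 15.4-point half-width.

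Much of this stands as a limit on scope: the hypothesis test is unaffected, and the distortion is small if few patients die or are transplanted first. It does not remove the point. If deaths are not censored, the plan still lacks a rule for them in its primary outcome. The categorical tests are not assigned to the primary end-point and do not estimate time to event. Wide sampling error does not excuse a bias that runs one way in each arm and does not shrink with sample size.

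One further caution also stands. Cumulative incidence can mislead if shown alone. In the equal-hazard simulation, the arm with more deaths and transplants shows less rebleeding (25.3% versus 28.7%) although carvedilol was given no effect on GVB. The remedy has to allow for that.

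**Conclusion.** The concern holds. Kaplan-Meier is the only time-to-event estimator named for GVB and UGIB, and death or transplantation before rebleeding is not addressed anywhere. If those patients are censored, as is usual, one minus Kaplan-Meier is never below the cumulative incidence and exceeds it once a rebleed follows a competing event in that arm.

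The direction in each arm is certain on that reading. The size is not known from the documents: under the constant hazards assumed here it runs from under 1 point to about 10 points at 2 years, and the arm difference can move either way. The effect is confined to the curves and to absolute risks taken from them. This should be fixed, because it concerns how the primary outcome is described and a better method is readily available, but it does not invalidate the planned test.

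**What to change.** Amend the Statistical analysis section as follows.

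- State that death and liver transplantation before rebleeding are competing events for GVB and UGIB, and state what counts as censoring.
- Estimate GVB and UGIB probabilities by Aalen-Johansen cumulative incidence in each arm, and show the cumulative incidence of death or transplantation beside them so that fewer rebleeds are not mistaken for benefit when more patients died first.
- Keep the log-rank test and Cox model, labelled as cause-specific analyses. Gray's test or a Fine-Gray model may be added as supportive.
- Kaplan-Meier is currently planned for mortality alone, whereas the secondary end-point is death or transplantation. Apply it to that composite, with transplantation counted as an event. If mortality alone is also analysed, say how transplantation is treated there.

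The cost is a few sentences and standard software. No new type of data is needed, because deaths and transplants, with their dates, are already required for the secondary end-point. The price is slightly more analysis, lower reported rebleeding percentages, arm differences that may shrink or grow, and the need to read two sets of curves together.
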